#### **10.5.4 Gastrointestinal events in relation to acute renal failure**

Acute renal impairment caused by dehydration is a potential risk described for other GLP-1 RA. Acute renal impairment is not thought to be caused directly by GLP-1 RA (including efpeglenatide) without dehydration.

In case of prolonged or severe nausea and vomiting, if clinically indicated, serum creatinine measurement should be performed at the central laboratory. If there is an acute increase of serum creatinine, metformin must be discontinued (if concomitantly taken) until resolution of renal dysfunction. Please also refer to Appendix 5 ([Section 10.5.1](#)), increase in serum creatinine flowchart for further recommendations.

#### **10.5.5 Guidance for monitoring participants with diabetic retinopathy**

[figure not shown]
Investigators are reminded that all participants should have eye examinations based on their retinopathy status, performed by a professional eye care provider according to International Council of Ophthalmology (ICO) guidelines or local standards; this should occur quarterly at a minimum for participants at high risk (eg, participants with severe non-proliferative diabetic retinopathy, proliferative diabetic retinopathy, and/or diabetic macula edema).

### **10.6 APPENDIX 6: COUNTRY-SPECIFIC REQUIREMENTS**

Not applicable.

### 10.7 APPENDIX 7: HYPOGLYCEMIA CLASSIFICATION

Figure 2 - Hypoglycemia classification

\*The patient is not able to treat her/himself because of the acute neurological impairment and requires another person to actively administer sugar, glucagon or intravenous glucose

PG: plasma glucose, SAE: serious adverse event

**10.8 APPENDIX 8: PATIENT QUALITATIVE ASSESSMENT OF TREATMENT VERSION 2**

[figure not shown]
The following questions ask for your opinion **on the drug you received during this clinical study**.

There are no right or wrong answers; we would like to better understand your own experience of the drug.

**1. During this trial, what were the main benefits you experienced with the drug you received?**

*Free-text*

**2. On a scale of 0 to 10, how beneficial was the drug you received during this trial?**

**3. During this trial, what were the main disadvantages you experienced with the drug you received?**

*Free-text*

**4. On a scale of 0 to 10, how disadvantageous was the drug you received during this trial?**

**5. After this trial, would you be willing to continue using the drug you received during this trial?**

Yes  No

**Please explain why?**

[figure not shown]
Free-text

**6. Based on your own experience in this trial, please select a response on the scale below**

[figure not shown]
 - 3	 - 2	 - 1	 0	 1	 2	 3
The disadvantages of the drug I received significantly outweigh the benefits			There were equal benefits and disadvantages of the drug I received			The benefits of the drug I received significantly outweigh the disadvantages

[figure not shown]

[figure not shown]
## **10.9 APPENDIX 9: PATIENT-REPORTED OUTCOMES MEASUREMENT INFORMATION SYSTEM (PROMIS) GASTROINTESTINAL SYMPTOM SCALES VERSION 1.0**

[figure not shown]
Last Updated: 1 September 2016  
© 2010-2016 PROMIS Health Organization and PROMIS Cooperative Group Page 1 of 2

## 10.10 APPENDIX 10: ABBREVIATIONS

ADA:	antidrug antibody
AE:	adverse event
AESI:	adverse event of special interest
ALT:	alanine aminotransferase
ANCOVA:	analysis of covariance
AST:	aspartate aminotransferase
BMI:	body mass index
BOCF:	baseline observation carried forward
BP:	blood pressure
CEC:	Clinical Endpoint Committee
CI:	confidence interval
CRF:	case report form
CRO:	contract research organization
CT:	computed tomography
CV:	cardiovascular
DMC:	Data Monitoring Committee
DPP-4:	dipeptidyl peptidase 4
DTP:	Direct-To-Patient
ECG:	electrocardiogram
eCRF:	electronic Case Report Form
eGFR:	estimated glomerular filtration rate
EOT:	end of treatment
FDA:	Food and Drug Administration
FPG:	fasting plasma glucose
FSH:	follicle stimulating hormone
GCP:	Good Clinical Practice
GI:	gastrointestinal
GLP-1:	glucagon-like peptide 1
GLP-1 RA:	glucagon-like peptide 1 receptor agonist
HbA1c:	hemoglobin A1c
HRT:	hormonal replacement therapy
IB:	Investigator's Brochure
ICF:	informed consent form
ICH:	International Council for Harmonisation
ICO:	International Council of Ophthalmology
IEC:	Independent Ethics Committee
IMP:	Investigational Medicinal Product
IRB:	Institutional Review Board
IRT:	interactive response technology
ITT:	intent-to-treat
MACE:	major adverse cardiovascular event
MDRD:	Modification of Diet in Renal Disease

MEN-2:	multiple endocrine neoplasia syndrome type-2
MI:	multiple imputation
MNAR:	missing not at random
MRI:	magnetic resonance imaging
MTC:	medullary thyroid cancer
NIMP:	noninvestigational medicinal product
OAD:	oral anti-diabetic
OC:	observed case
PEG:	polyethylene glycol
PK:	pharmacokinetic
popPK:	population PK
PQATv2:	Patient Qualitative Assessment of Treatment version 2
PRO:	patient-reported outcome
PROMIS:	Patient-Reported Outcome Measurement Information System
PTC:	Product Technical Complaint
SAE:	serious adverse event
SAP:	statistical analysis plan
SC:	subcutaneous
SD:	standard deviation
SE:	standard error
SGLT2:	sodium/glucose cotransporter 2
SMPG:	self-monitored plasma glucose
SoA:	Schedule of Activities
SUSAR:	suspected unexpected serious adverse reaction
T2DM:	type 2 diabetes mellitus
TEAE:	treatment-emergent adverse events
UB:	upper bound
ULN:	upper limit of normal
WOCBP:	women of childbearing potential

## **10.11 APPENDIX 11: PROTOCOL AMENDMENT HISTORY**

[figure not shown]
The Protocol Amendment Summary of Changes Table for the current amendment is located directly before the Table of Contents (TOC).

## LIST OF ABBREVIATIONS AND DEFINITION OF TERMS

|         |  |
|---------|--|
| ADA:    | anti-drug antibody                             |
| AE:     | adverse event                                  |
| AERSM:  | adverse event requiring specific monitoring    |
| AESI:   | adverse events of special interest             |
| ALT:    | alanine aminotransferase                       |
| BMI:    | body mass index                                |
| CMH:    | Cochran-Mantel-Haenszel                        |
| ECG:    | electrocardiogram                              |
| EOS:    | end of study                                   |
| EOT:    | end of treatment                               |
| GI:     | gastrointestinal                               |
| HbA1C:  | hemoglobin A1c                                 |
| HLGT:   | high-level group term                          |
| HLT:    | high-level term                                |
| IMP:    | Investigational Medicinal Product              |
| IRT:    | Interactive Response Technology                |
| LLT:    | lower-level term                               |
| mITT:   | modified intent-to-treat                       |
| NIMP:   | noninvestigational medicinal product           |
| PCSA:   | potentially clinically significant abnormality |
| PRO:    | patient reported outcome                       |
| PT:     | preferred term                                 |
| R:      | randomization                                  |
| SAE:    | serious adverse event                          |
| SOC:    | system organ class                             |
| T2DM:   | Type 2 diabetes mellitus                       |
| TEAE:   | treatment-emergent adverse event               |
| UB:     | upper bound                                    |
| WHO-DD: | World Health Organization-Drug Dictionary      |

# 1 OVERVIEW AND INVESTIGATIONAL PLAN

## 1.1 STUDY DESIGN AND RANDOMIZATION

This is a Phase 3, multicenter, 56-week, randomized, open-label for the drug (efpeglenatide and dulaglutide) and double-blind for the doses of efpeglenatide, active-controlled, 3-arm, parallel group study in participants with type 2 diabetes mellitus (T2DM) inadequately controlled with metformin.

After a Screening phase of up to 3 weeks, participants will be centrally randomized (using permuted block randomization schedule) via Interactive Response Technology (IRT) in a 1:1:1 ratio to 1 of the following 3 treatment groups:

- efpeglenatide 4 mg
- efpeglenatide 6 mg
- dulaglutide 1.5 mg

Randomization will be stratified by Screening hemoglobin A1c (HbA1c) ( $<8.0\%$ ,  $\geq 8.0\%$ ) and Visit 3 (Baseline, Day 1) body mass index (BMI) ( $<30 \text{ kg/m}^2$  and  $\geq 30 \text{ kg/m}^2$ ). Participants will receive open-label, active-controlled treatment for 56 weeks. Additional details on the study design and plan are provided in [Section 1.4](#).

Approximately 900 participants (300 participants per treatment group [details in [Section 1.3](#)] will be randomized.

## 1.2 OBJECTIVES

### 1.2.1 Primary objectives

The primary objective of this study is to demonstrate the noninferiority of once-weekly injection of efpeglenatide 4 or 6 mg in comparison to once-weekly injection of dulaglutide 1.5 mg on HbA1c change from Baseline to Week 56 in participants with T2DM inadequately controlled with metformin.

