#### **2.3.1.2 Modified Intent-to-treat population**

Due to the study terminated early by sponsor on September 9, 2020 (hereinafter referred to as “early termination”), the efficacy analyses will be performed in mITT population instead of ITT population originally planned. The mITT population is defined as,

- Participants who have completed the study treatment, or
- Participants who discontinued the study treatment AND completed/discontinued the study before the early termination, or
- Participants who discontinued treatment before early termination and discontinued the study due to early termination within 30 days of the target Week 56 visit (Day 392), or
- Participants who discontinued treatment due to early termination within 30 days of the target Week 56 visit (Day 392).

Participants will not be included in mITT if they discontinued study due to termination and discontinued study treatment (before or due to early termination) and had visits performed more than 30 days before the target Week 56 visit (Day 392).

By-visit summary will be provided for ITT population in addition for mITT population.

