#### **2.4.4.1 Analysis of primary efficacy endpoint**

##### **Hypothesis Testing of the Primary Endpoint:**

For the primary efficacy variable of change from Baseline to Week 56 in HbA1c, the following statistical null hypothesis and alternative will be tested as:

- H0: efpeglenatide - dulaglutide  $\geq$  0.3%
- H1: efpeglenatide - dulaglutide  $<$  0.3%

The null hypothesis will be tested at a 1-sided alpha level of 0.025 using a non-inferiority margin of 0.3%.

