##### **Primary Analysis:**

The statistical analysis for the primary endpoint is described below.

The Baseline value is defined in [Section 2.1.1](#).

Analysis of the primary efficacy endpoint (change from Baseline to Week 56 in HbA1c) will be performed using the ITT population, using HbA1c measurements obtained during the study, including those obtained after IMP discontinuation or introduction of rescue therapy.

The primary efficacy endpoint of change in HbA1c from Baseline to Week 56 will be analyzed with missing values imputed by BOCF-like MI method for both efpeglenatide and dulaglutide groups, under the MNAR framework:

- For participants with missing HbA1c values at Week 56, the missing values will be imputed using a random draw from a normal distribution with mean equal to their Baseline HbA1c and the standard deviation equal to the pooled standard deviation calculated from the square root of the mean square error estimated from a regression model with Baseline HbA1c as the dependent variable and randomization strata and treatment as the covariates.

In this analysis, missing endpoint values will be imputed 10 000 times to generate 10 000 data sets with complete data. Each of the complete datasets after the imputation will be analyzed by the ANCOVA model with the treatment groups (efpeglenatide 4 or 6 mg, dulaglutide 1.5 mg), randomization stratum of screening HbA1c ( $<8.0$ ,  $\geq 8.0\%$ ), Visit 3 (Day 1) BMI ( $<30$  and

$\geq 30 \text{ kg/m}^2$ ), and geographical region (North America, Eastern Europe (including Hungary and Poland)) as fixed effects, and baseline HbA1c value as a covariate.

In case a baseline value needed for multiple imputations is missing, it will be imputed by the population mean at Baseline.

SAS pseudo-codes are provided in [Appendix A](#).

Results from each complete dataset will be combined to provide the adjusted mean change in HbA1c from baseline to Week 56 (regardless of treatment discontinuation or initiation of rescue therapy) for each treatment group, as well as the between-group difference (comparing each efpeglenatide group versus dulaglutide group) and the 95% CI for the difference. This will be implemented using MIANALYZE procedure in SAS. If the UB of the 2-sided 95% CI for the adjusted mean difference (efpeglenatide versus dulaglutide) in HbA1c change from baseline to Week 56 is  $\leq 0.3\%$ , the noninferiority will be declared.

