If noninferiority is demonstrated on the primary endpoint for both efpeglenatide groups, ie, the UB of the 2-sided 95% CI  $\leq 0.3\%$ , the superiority of each efpeglenatide group versus dulaglutide for the primary endpoint will be tested in a hierarchical fashion, with efpeglenatide 6 mg tested first and then efpeglenatide 4 mg.

Summary statistics (for screening value, Baseline value, observed values, and observed changes from Baseline) at scheduled visits will be provided for each treatment group. The summary will include the number of observations, mean, SD, SE, minimum, median, and maximum. Graphical presentations will also be used to examine trends over time using mean values ( $\pm$ SE) and mean changes from Baseline ( $\pm$ SE) at each of the scheduled visits (using OC).

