### **Sensitivity Analysis:**

#### ***Tipping point analysis:***

Tipping point analysis based on the same multiple imputation (MI) method as applied above will be performed to examine the robustness of the results from the primary analysis. A penalty  $\delta$  will be added to participants in efpeglenatide groups (4 or 6 mg) who have no HbA1c data at Week 56. The penalty will be gradually increased to evaluate at which level the conclusion of the analyses in terms of non-inferiority is changed for each efpeglenatide dose group. The tipping point is the penalty level at which the magnitude of efficacy reduction in participants without HbA1c data at Week 56 creates a shift in the treatment effect of efpeglenatide from the demonstration of non-inferiority to the failure of non-inferiority. The penalty  $\delta$  will start at 0 and increase by 0.1 (unit: %) at each imputation until UB of the 2-sided 95% CI for the adjusted mean difference is  $> 0.3\%$ . Least square mean difference between each efpeglenatide dose and dulaglutide and their associated 95% CI will be provided for each penalty level.

SAS pseudo-codes are provided in [Appendix A](#).

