#### **2.4.4.3 Multiplicity issues**

After noninferiority for the primary endpoint of change in HbA1c from Baseline to Week 56 has been established for both efpeglenatide 4 and 6 mg, the secondary endpoints will be tested in the prioritized order as follows:

1. Change from baseline to Week 56 in HbA1c for efpeglenatide 6 mg versus dulaglutide (Superiority)
2. Change from baseline to Week 56 in body weight for efpeglenatide 6 mg versus dulaglutide (Superiority)
3. HbA1c <7.0% at Week 56 for efpeglenatide 6 mg versus dulaglutide (yes/no) (Superiority)
4. Change from baseline to Week 56 in body weight for efpeglenatide 4 mg versus dulaglutide (Superiority)
5. Change from baseline to Week 56 in HbA1c for efpeglenatide 4 mg versus dulaglutide (Superiority)
6. HbA1c <7.0% at Week 56 for efpeglenatide 4 mg versus dulaglutide (yes/no) (Superiority)
7. Change from baseline to Week 56 in FPG for efpeglenatide 6 mg versus dulaglutide (Superiority)

8. Change from baseline to Week 56 in FPG for efpeglenatide 4 mg versus dulaglutide (Superiority)

The testing will stop as soon as an endpoint for an efpeglenatide dose is found to be not statistically significant at  $\alpha=0.05$  (2-sided). No multiplicity adjustment will be made on other secondary efficacy variables or the comparison of other efpeglenatide dose versus dulaglutide than those mentioned earlier in this section.

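### The two primary noninferiority tests have no order or alpha adjustment, so a claim for one dose alone could exceed the stated one-sided 2.5% level

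*SAP*

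**What the plan says.** - **Objective.** SAP 1.2.1 sets out "to demonstrate the noninferiority of once-weekly injection of efpeglenatide 4 or 6 mg in comparison to once-weekly injection of dulaglutide 1.5 mg". Protocol Table 1 has the same objective.
- **Hypothesis.** SAP 2.4.4.1 and protocol 9.1 write one null hypothesis for efpeglenatide minus dulaglutide, without naming a dose: "The null hypothesis will be tested at a 1-sided alpha level of 0.025 using a non-inferiority margin of 0.3" percent HbA1c.
- **Declaration rule.** The primary analysis in SAP 2.4.4.1 reports adjusted means "as well as the between-group difference (comparing each efpeglenatide group versus dulaglutide group) and the 95% CI for the difference". If the upper bound of the two-sided 95% interval is at most 0.3%, "the noninferiority will be declared". The protocol synopsis and protocol Table 5 carry the same rule.
- **Where both doses are needed.** The same section continues to superiority with "If noninferiority is demonstrated on the primary endpoint for both efpeglenatide groups", and then takes 6 mg before 4 mg. SAP 2.4.4.3 opens its eight-step list with "After noninferiority for the primary endpoint of change in HbA1c from Baseline to Week 56 has been established for both efpeglenatide 4 and 6 mg". Protocol Table 5's matching row has MI where the SAP has noninferiority; the primary-endpoint row of that table shows that noninferiority is meant.
- **Sensitivity analysis.** The tipping-point analysis is run "to evaluate at which level the conclusion of the analyses in terms of non-inferiority is changed for each efpeglenatide dose group".
- **Analysis set.** After early termination, SAP 2.3.1.2 says "the efficacy analyses will be performed in mITT population instead of ITT population originally planned". It gives no count for that set.

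**The concern.** The rule for declaring noninferiority is applied to two contrasts, each at one-sided 0.025. The requirement that both doses pass appears only as the condition for going on to superiority, and the 6-then-4 mg order and the eight steps cover superiority only. No section says whether noninferiority of one dose may be claimed when the other fails or, if it may, at what level.

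Two things are at stake. If a single-dose claim is allowed, the primary family has two chances of a false claim at 2.5% each, and its error can exceed the level the SAP states. And if the result is split, choosing between an either-dose and a both-doses rule after seeing it would be post hoc, although either can be defended if fixed in advance.

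**Working it through.** **Inputs.** Margin 0.3% and one-sided alpha 0.025 (SAP 2.4.4.1); SD 1.1%, true difference 0, 300 per arm and 91% power (SAP 1.3); 1:1:1 allocation (SAP 1.1). With equal arms, a shared control and a common SD, the two test statistics have correlation 0.5. Normal approximation, full data.

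**1. The plan's own figure.** SE = 1.1 × √(2/300) = 0.0898. Power = Φ(0.3/0.0898 − 1.960) = Φ(1.380) = 91.6%. The stated 91% reproduces, and it is the power for one dose against dulaglutide.

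**2. Error if one dose may be claimed alone, both doses at the margin.** P(at least one false claim) = 0.025 + 0.025 − P(both pass).
- Correlation 0.5: 0.05 − 0.0046 = 0.0454
- Correlation 0.4: 0.0466
- Correlation 0.6: 0.0438
- Upper limit for any correlation: 0.05

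**3. Error away from that point** (300 per arm, correlation 0.5), one dose at the margin:
- Other dose 0.05 beyond it: shift 0.05/0.0898 = 0.557 SE; 0.0250 + 0.0059 − 0.0016 = 0.0293.
- Other dose 0.10 beyond it: shift 1.113 SE; 0.0250 + 0.0011 − 0.0004 = 0.0257.
- Other dose truly noninferior: only one claim can be false, so at most 0.025.
- Both doses required: at most 0.025.

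**4. Power and the chance of a split result**, true difference 0. Exactly one dose passing = (at least one) − (both). The sizes 250 and 200 are assumptions, because the documents give no number for the mITT set.

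| Per arm | At least one, as written | At least one, Hochberg | Both doses | Exactly one, as written |
|---|---|---|---|---|
| 300 | 97.5% | 95.5% | 85.8% | 11.7% |
| 250 | 94.9% | 91.5% | 77.5% | 17.4% |
| 200 | 89.9% | 84.4% | 65.8% | 24.1% |

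**5. Error under the remedies.** A fixed sequence, each step at one-sided 0.025, keeps the familywise error at or below 0.025. Hochberg gives 0.0240 with both doses at the margin (0.0244 and 0.0235 at correlations 0.4 and 0.6).

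**6. What Hochberg changes in practice.** At 300 per arm, the largest observed difference that permits a single-dose claim is 0.3 − 1.960 × 0.0898 = 0.124 now, and 0.3 − 2.241 × 0.0898 = 0.099 under Hochberg.

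**The case against.** The best defence is that the plan means both doses to pass. The only text on what follows from noninferiority requires both, and the SAP's multiplicity section opens with that condition. On that reading the error is at most 2.5% and one clarifying sentence is enough.

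A reader might infer from the wording *4 or 6 mg* in the objective that the sponsor intends to claim either dose. The documents do not support so firm a reading. They use the same phrase as a label for both arms: in the ANCOVA treatment factor, in the tipping-point penalty, and in the description of the dose levels in protocol 4.1. The phrase does not settle the matter.

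A reader might also infer that the trial runs at a 4.5% error rate, or that the superiority claims are exposed. Neither follows. The 4.5% requires that a stand-alone claim be allowed and that both doses lie exactly at the margin. Protocol 4.3 expects 6 mg to be more effective than 4 mg, so that is not the expected case. The superiority tests sit behind the both-doses gate and then run in fixed order.

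What remains is the rule as written. It declares noninferiority from an unadjusted interval computed for each dose, the tipping-point analysis treats the conclusion dose by dose, and the both-doses condition is never attached to the declaration itself. A single-dose claim is therefore permitted by the rule, although nowhere stated.

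**Conclusion.** The point holds in a limited form. The rule in SAP 2.4.4.1 allows a single-dose noninferiority claim, and no order or adjustment covers the two tests. If such a claim is made, the familywise error reaches 4.5% at worst against the stated one-sided 2.5%. It falls quickly as one dose moves beyond the margin, and it does not exceed 2.5% if either dose is truly noninferior or if both are required.

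The split outcome is not remote: on the planning assumptions about one trial in nine would end with exactly one dose passing, and more if fewer than 300 per arm are analysed. These figures rest on SD 1.1%, a common variance, equal arms and full data. This should be settled before database lock; it does not undermine the rest of the testing scheme.

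**What to change.** Before database lock, amend the declaration sentence in SAP 2.4.4.1 and add a matching paragraph at the start of 2.4.4.3, so that the two do not conflict. Choose one rule:

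- **(a) Fixed sequence.** Test 6 mg, then 4 mg only if 6 mg passes, each on the two-sided 95% upper bound. This matches the order already used for superiority on HbA1c. Planning power stays at 91.6% for 6 mg and 85.8% for both. Cost: 4 mg cannot be claimed if 6 mg fails.
- **(b) Hochberg at one-sided 0.025.** Declare both doses if both 95% upper bounds are at most 0.3%; otherwise declare a single dose only if its two-sided 97.5% upper bound is at most 0.3%. Cost: power for at least one dose falls from 97.5% to 95.5% at 300 per arm (from 94.9% to 91.5% at an assumed 250, and from 89.9% to 84.4% at 200). Power for both doses is unchanged.
- **(c) Both doses required.** If that is the intention, say so in both sections. No adjustment is needed, but SAP 1.3 should state that 91% is the power for one comparison and that joint power is 85.8%.

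The tipping-point rule should use whichever bound supported the declaration. Record the change in SAP Table 1 (section 1.6) as a departure from the rule in the protocol synopsis and protocol Table 5, because some results that count as noninferior for a single dose under that rule would no longer do so. Keep the both-doses gate and steps 1 to 8 as they are. The work is a small SAP edit; option (b) needs only a wider interval from the same imputed datasets, pooled estimate and standard error.
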